A technology-based approach using computers and mobile devices (smart phones and tablets) promises to meet this necessity with high flexibility and accessibility, and minimizes the cost of the intervention in busy health care settings. Also, a technology-based intervention that does not involve face-to-face interactions could work better for many women from cultures where breast cancer is still a stigmatizing experience. Bespite the high potential, few technology-based interventions are available for ethnic minority breast cancer survivors, especially for Asian Americans. Therefore, based on Preliminary Studies (PSs), the research team has developed and pilot-tested a theory-driven technology-based information and coaching/support program that: (a) is tailored to Asian American breast cancer survivors by incorporating actual data on individual sub-ethnic groups cultural attitudes from PSs; (b) uses multiple languages; (c) provides both group and individual (real-time and personalized) coaching/support by culturally matched bilingual health care providers; (d) incorporates peer support through a social media function; and (e) integrates existing general and culture-specific evidence-based educational content from scientific authorities. Among over 71 sub-ethnic

groups of Asian Americans,⁴⁶ only three sub-ethnic groups (Chinese, Korean, and Japanese) were selected for the program development for the convenience of the approach (e.g., language). Within Asian Americans, Chinese are the largest sub-ethnic group,^{47,48} Koreans are the fastest growing sub-ethnic group,^{47,48} and Japanese are the sub-ethnic group at the highest risk of breast cancer.^{1,2,11,49}

Goals/Aims

The purpose of the proposed randomized intervention study is to test the efficacy of the technology-based information and coaching/support program for Asian American breast cancer survivors (TICAA) in enhancing the women's breast cancer survivorship experience.

The **specific aims** of the study are to:

Aim 1. Determine whether the intervention group (who uses the TICAA and the information on breast cancer by the American Cancer Society [ACS]) will show significantly greater improvements than the control group (who uses only the information on breast cancer by the ACS) in **primary outcomes** of the TICAA (needs for help, physical and psychological symptoms, and quality of life) from baseline (pre-test) to Time Points 1 (post 1-month; primary) and 2 (post 3-months; secondary).

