Aim 2. Identify theory-based variables (attitudes, self-efficacy, perceived barriers, and social influences related to breast cancer survivorship) that **mediate** the intervention effects of the TICAA on the primary outcomes of the TICAA from baseline to Time Point 1.

Aim 3 (exploratory). Explore whether the effects of the TICAA on the primary outcomes are **moderated** by background factors and disease factors.

Study Design

Organizational structure of the study team:

This is a PI initiated R01 research project that is funded by the National Cancer Institute (National Institute of Health). Due to PI's move from Duke University to Emory University, the study is being transferred from Duke Univ. to Emory University. This is the fourth year of the total 5 year of funding. This IRB approval is needed for the grant transfer.

The study team includes the PI, 1 Co-Investigator, 1 Statistician, multiple Consultants, 3 interventionists and 1 or 2 research assistants. Except the consultants, all research team members will be Emory affiliated. The research team will conduct the study at School of Nursing, Emory University.

Setting and location:

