The data are mainly collected through the Internet survey questionnaire. When potential participants visit the project Web site (after receiving/reviewing a study announcement), they will be asked to review the informed consent. When participants click I agree to participate, they will have given their consent. Then, after checking them against the inclusion criteria and quota requirements, only those who meet the criteria and requirements will be automatically assigned a serial number, and randomized into two groups using an automated random number generator accessible through the Web site.

Then, the women will be asked to fill out the Internet survey questionnaire (if requested, paper-and-pencil questionnaires will be provided/used, or research staff will assist in administering the Internet surveys over the phone.) and sign up the Web site by creating their own ID and passwords. Whenever they visit the Web site, they need to use the ID and passwords to log in the site. If they want, they can change their ID and passwords. Then, both groups will be provided with an electronic instruction sheet on when they need to come back and fill out additional questionnaires and/or use the program.

Biweekly, the research team will send reminders and thank-you emails. Two weeks before the end of the 1st month, both groups will be asked to fill out the next set of the instruments by the end of the 1st month. Then, 2 weeks before the end of the 3rd month, both groups will be asked to fill out the next set of the instruments by the end of the 3rd month.

O Description of research instruments to be used (e.g., questionnaires, surveys, interview or focus group guides, scales)

Multiple instruments will be used: the Support Care Needs Survey-34 Short Form (SCNS-34SF),⁵⁰ the Memorial Symptom Assessment Scale-Short Form (MSAS-SF),⁵¹ the Functional Assessment of Cancer Therapy Scale-Breast Cancer (FACT-B),⁵² the modified Questions on Attitudes, Self-Efficacy, Perceived Barriers, and Social Influences (QASPS),⁵³ the Cancer Behavior Inventory (CBI),^{54,55,56} the Perceived Isolation Scale (PIS),^{57,58} the Personal Resource Questionnaire (PRQ-2000),⁵⁹ and 27 questions on background characteristics, level of acculturation, and disease factors. The reliability and validity of all the instruments have been established among Asian Americans. Cronbach's alpha of individual instrument ranged from .76 to .96 among Asian Americans.

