Aim #1: Effects on Primary Outcomes. Separate intent-to-treat general linear models 86 will be used to examine differences in continuous outcome measures by intervention group at each time point, adjusting for baseline outcome and any variables that demonstrate imbalances in preliminary analyses. Model assumptions will be assessed, and modifications will be implemented as necessary to improve mode fit. Differences in continuous outcome measures over time will be examined using an intent-to-treat linear mixed-model growth curve analysis with SAS Proc Mixed.86 Mixed models will be used in which all available data collected during follow-up is used.87,88 Separate mixed effects regression models will be generated for each outcome measure. Both random slopes and intercepts will be modeled to represent the subject level deviation from the average, or fixed-effect, slope over time and intercept, respectively. Restricted maximum likelihood estimation will be used, and the most appropriate covariance structure will be examined. The outcomes will be analyzed as repeated observations of the dependent variables, with mean-centered baseline outcome scores serving as a covariate. Other predictors will include intervention group, time from baseline to follow-up, the interaction of group and time, and the interaction of baseline measures and time. Baseline outcome and group will be analyzed as time-independent covariates. Other demographic or treatment timeindependent variables identified in preliminary analyses may be included as covariates. Main effects and higher order interaction terms will be examined. The Akaike information criterion will evaluate overall model fit and to select the best-fitting longitudinal change pattern.89

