Aim #3: Moderation of Intervention Effects. The moderating role of background and disease factors will be generated for each outcome. Intention-to-treat mixed-modeling procedures86 as described above will be used to test and estimate differences in outcome across intervention groups and how moderators modify such differences. Accordingly, coefficient estimates for these measures by time represent the extent to which mediators affect slopes of change for outcome across time. Initial models will include all main effects and possible two- and three-way interactions between moderator, intervention group, and time. With respect to random effects, in addition to random intercepts, random slopes for time, moderator variables will be estimated to account for within-individual variability. As before, each model will control for baseline outcome values, which will be centered about the grand mean for all patients. Accordingly, intercepts represent the mean baseline outcome score across patients, adjusting for all other values included in the respective models.

Training of study team

All research team members will complete CITI training before engaged in the study. Also, to eliminate contamination across interventionists and minimize risk of differential treatment delivery among different interventionists, the interventionists will be trained by the PI with the intervention protocol developed through PSs. The interventionists' first 5 messages through the social media sites and the chat function will be monitored and evaluated by the research team, and the team's feedback will be incorporated into their subsequent coaching/support. Also, the interventionists will learn methods of facilitating discussions without influencing participants and helping women to set goals and solve problems. Two culturally-matched RAs will be trained on the logistics for the participant recruitment, the online survey system, and the delivery of the online questionnaires. Team meetings will be held monthly to address problems, reinforce learning, and monitor progress. Retraining of the interventionists and RAs will be done every 18 months to prevent drift.

Plans for Monitoring the Study for Safety

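### The Aim 3 mixed model puts random slopes on time and on moderators that are mostly constant within a woman, which two follow-up values per woman cannot support as written

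*Combined protocol and SAP*

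**What the plan says.** The section on Aim 3 (Moderation of Intervention Effects) sets out both halves of the model. For the fixed part, "Initial models will include all main effects and possible two- and three-way interactions between moderator, intervention group, and time". For the random part, besides random intercepts, "random slopes for time, moderator variables will be estimated to account for within-individual variability". It refers back to the mixed-model procedures of Aim 1.

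Three other statements fix what data that model sees:

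- **Moderators.** Under Goals/Aims, the question is whether effects "are moderated by background factors and disease factors". The list of research instruments gives the source as "27 questions on background characteristics, level of acculturation, and disease factors".
- **Outcome occasions.** Aim 1 looks at change "from baseline (pre-test) to Time Points 1 (post 1-month; primary) and 2 (post 3-months; secondary", so there are two follow-ups.
- **Baseline.** The Aim 1 analysis section says "The outcomes will be analyzed as repeated observations of the dependent variables, with mean-centered baseline outcome scores serving as a covariate". Aim 3 repeats this: "each model will control for baseline outcome values, which will be centered about the grand mean for all patients". Each woman therefore contributes at most two values of the dependent variable.

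The Aim 1 section also specifies a random intercept and a random time slope, fitted by REML. It leaves the covariance structure to be examined and uses AIC for overall fit and for the pattern of change. Neither section says how the random effects are to be reduced if they cannot all be estimated.

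**The concern.** There are two separate faults.

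The first is conceptual. A random slope lets the effect of a covariate differ between women, and it is learned from women in whom the covariate takes more than one value. Where a background or disease factor has one value per woman, there is nothing within her to learn from, and the term cannot serve its stated purpose.

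The second is a matter of counting. Two outcome values per woman give a 2x2 covariance matrix with three distinct elements. A random intercept, a random time slope, their covariance and a residual variance already ask for four quantities, before any moderator slope is added.

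At stake is whether the stated analysis can be run as described. If it cannot, someone must decide which variance terms to keep, with the data in view, for each outcome and moderator. Some of those choices change the standard error of the moderation contrast.

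**Working it through.** The plan gives no figure for the Aim 3 model, so there is none to reproduce.

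**Inputs.** Outcome times t = 1 and 3 months, with baseline as covariate (Goals/Aims; Aim 1 and Aim 3 analysis sections). Random intercept, time slope and moderator slope (Aim 3). The moderator x is taken as constant within a woman. This is an inference, supported by Aim 1 treating demographic and treatment covariates as time-independent. Expected completers: 330 × (1 − 0.35) = 214.5, about 214.

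**Step 1: intercept and time slope, unstructured.** Let the intercept variance be a, the slope variance b, their covariance c and the residual variance s.

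- Variance at month 1: a + 2c + b + s
- Covariance of months 1 and 3: a + 4c + 3b
- Variance at month 3: a + 6c + 9b + s

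There are three equations and four unknowns. For any small d, changing s by +d, c by +d, a by −2.5d and b by −0.5d leaves all three unchanged:

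- Month 1: −2.5d + 2d − 0.5d + d = 0
- Covariance: −2.5d + 4d − 1.5d = 0
- Month 3: −2.5d + 6d − 4.5d + d = 0

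So there are 4 parameters and rank 3.

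**Step 2: add one moderator slope, unstructured.** Let its variance be m, its covariance with the intercept p and with the time slope q. The element for times j and k gains x²m + 2xp + xq(j + k). Every added term depends on x, so the slope only makes the covariance matrix differ between women with different moderator values. Parameters: 6 random-effect elements + 1 residual = 7.

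- Two-level moderator coded 0/1: x² = x, so only m + 2p and q can be learned. Rank 3 + 2 = 5.
- Three-level score or continuous moderator: m, p and q separate. Rank 3 + 3 = 6.

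A numerical rank check of the covariance derivatives gave the same 3, 5 and 6.

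**Step 3: diagonal structure (c = p = q = 0).** Intercept and time slope plus residual has 3 parameters and rank 3, just identified. Adding the moderator variance gives 4 parameters. The rank is 4 with 0/1 or continuous coding. It is 3 with −1/+1 coding, because x² = 1 for every woman and m cannot be told from a. Identification then depends on an arbitrary coding.

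This structure is also restrictive. Month-3 variance minus month-1 variance equals 8b. If the observed variance is smaller at month 3, b is held at zero and the fit becomes an equal-variance model. With complete data, each variance is then replaced by their average, (V1 + V3)/2.

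- Time Point 1 contrast: its SE is multiplied by √[(1 + V3/V1)/2], which is below 1.
- Three-way term: its SE depends on V1 + V3 − 2·cov, which the averaging preserves, so it does not move.

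**Step 4: size.** Four simulated cases were fitted under assumed covariances, since the documents give none. The diagonal structure hit the boundary in three. SE of the group-by-moderator contrast at Time Point 1:

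| Unstructured 2x2 | Diagonal | Shortfall |
|---|---|---|
| 0.288 | 0.278 | 1 − 0.278/0.288 = 3.5% |
| 0.260 | 0.231 | 1 − 0.231/0.260 = 11.2% |
| 0.348 | 0.298 | 1 − 0.298/0.348 = 14.4% |

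The three-way SE was unchanged. By the formula in Step 3, a 3.5% shortfall corresponds to V3/V1 = 2(0.278/0.288)² − 1 = 0.86, and a 14.4% shortfall to 2(0.298/0.348)² − 1 = 0.47. The upper end needs month-3 variance to be about half that at month 1.

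**Step 5: fixed effects.** One two-level moderator needs an intercept, 3 main effects, 3 two-way terms and 1 three-way term, which is 8. Baseline and baseline-by-time make 10. About 214 women can support that.

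**The case against.** **Fixed-effect inference does not need separate variance components.** It needs only the marginal covariance, and that stays identified under the unstructured form. In two simulated datasets of 214 women, REML fits of the 4-parameter model from three starting points gave different components each time. The likelihood and SEs were nonetheless identical, and equal to those of an unstructured 2x2 (three-way SE 0.1620 and 0.1316). The 7-parameter model gave the same three-way SEs, and group-by-moderator SEs of 0.4068 against 0.4066 and 0.3783 against 0.3782. This stands. A reader might infer that the fit must fail, or that the moderation SEs are arbitrary. Under the unstructured form they are not; the SE effect appears under the diagonal form.

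**The covariance structure is left open.** That is true, and a diagonal intercept and time slope is just identified. But no choice of structure makes a within-woman constant informative about within-woman variability, and with the moderator slope added the diagonal form depends on coding. Calling these initial models and mentioning AIC is not a rule for reducing the random effects.

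**Some disease factors may change.** The plan does not say that every one is measured once, and women in treatment are eligible. Even a factor measured again at both follow-ups would leave an intercept, two slopes and a residual resting on two outcome values.

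**Completion times vary.** Assuming times uniform over each two-week window, the unstructured intercept and time slope becomes formally identified, but weakly. With 214 women and assumed true variances of 0.40 and 0.03, the SEs are 0.40 and 0.09. A two-level moderator slope still fails (7 parameters, rank 6).

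**Baseline might be meant as a third occasion.** Aim 3 does describe intercepts as mean baseline scores. The time slope would then be identified (4 parameters, rank 4), as would an unstructured slope for a three-level or continuous moderator (7, rank 7). A two-level one would not (7, rank 6). Both analysis sections, however, make baseline a covariate.

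**Conclusion.** The concern holds for the random part of the Aim 3 model. The moderator slope cannot do what the plan says it is for. With two common follow-up times, the unstructured random effects exceed what the data identify by 1 parameter without a moderator slope, and by 1 or 2 with one. The fit may warn, return non-unique variance components or stop at a boundary. Under a diagonal structure that reaches the boundary, the SE of the Time Point 1 contrast was about 3% to 14% too small in the simulated cases, and the three-way SE was unaffected.

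Two stronger readings are not supported. One is that the interactions over-parameterise the model: for a single moderator they are estimable, and they would become heavy only if many moderators were entered together. The other is a comparison of 7 parameters with the 3 elements of one common 2x2 matrix. The moderator slope lets the matrix vary with the moderator, so the right comparison is with 5 or 6.

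The conclusion rests on moderators being mostly constant within a woman, on baseline being a covariate, and on common follow-up times. The percentages rest on assumed covariances. Severity is low, because Aim 3 is exploratory and no primary conclusion depends on it. The time-slope part of the problem begins in the Aim 1 mixed model, from which Aim 3 takes its procedures.

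**What to change.** 1. In Aim 3, delete the random slopes for moderators. Replace the random intercept and time slope with an unstructured 2x2 covariance over months 1 and 3, which has 3 parameters and is exactly identified.
2. Make the same covariance change in the Aim 1 mixed model, so that Aim 3's reference back to it still works.
3. Keep the group, moderator and time main effects with all their two- and three-way interactions, and state that each model contains one moderator.
4. Report both the group-by-moderator contrast at Time Point 1 and the three-way change-over-time term, with confidence intervals, labelled exploratory. Reporting both keeps the plan's interest in change over time.
5. Correct the sentence describing intercepts as mean baseline scores, so that it agrees with baseline being a covariate.

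The cost is analysis-plan wording and a simpler model. No data collection or sample size changes.

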
o Confidentiality:

All e-mail/Internet communication between participants and the research team will be kept confidential by saving e-mails on the study team secure server with restricted access only to research team members. All e-mails received or sent by participants or the research team and other identity information will not be shared with others, and they will be on a firewall-protected computer to which only the research team can access. Also, at the completion of the study, the saved e-mails will be permanently destroyed to ensure confidentiality. In addition, as described earlier, e-mail addresses will be used only for reminders and participation compensation, and will be kept separate from other participant data. Furthermore, their email addresses will be accessed only by the research team, and the participants can communicate with other participants only through the social media sites (no email address will be disclosed to other participants).

As described above, the data that the participants will provide will not include any information linked to their identities except email addresses, and only research staff will have access to the data. E-mail addresses will be used only for the reminders and reimbursement. As explained above, at the completion of the study, the saved e-mails will be permanently destroyed to ensure confidentiality.

References

- 1. National Cancer Institute. SEER Stat Fact Sheets: Breast. http://seer.cancer.gov/statfacts/html/breast.html. Accessed December 31, 2013.
- 2. American Cancer Society. Cancer facts and figures, 2013. http://www.cancer.org/research/cancerfactsfigures/cancerfactsfigures/cancer-facts-figures-2013. Accessed December 31, 2013.
- 3. U.S. Department of Health and Human Services. Office of Minority Health. Cancer data/statistics. http://minorityhealth.hhs.gov/templates/browse.aspx?lvl=3&lvlid=4. Accessed December 31, 2013.
